### **Restricted Therapies/Products**

Subjects are permitted to receive the following only when absolutely necessary:

- Investigators' discretion/clinical judgement is recommended in accordance with the institutional guidelines for the following:
  - Prophylactic or supportive treatment for expected toxicities, including management of study drug;
  - Hematopoietic growth factors used for prophylaxis or treatment;
  - Bisphosphonates (eg, pamidronate or zoledronate) or denosumab for pain management and palliation of bony metastases, or treatment of osteoporosis.
- Subjects who wear contact lenses must discontinue wearing their lenses if they have any mild to moderate eye symptoms (CTCAE Grade  $\leq 2$ ) while receiving treatment until at least 1 week after symptoms have resolved. If a subject has a recurrence of eye symptoms or experiences any severe (CTCAE Grade  $\geq 3$ ) ocular events they must discontinue wearing their contact lenses until at least 1 week after treatment is permanently discontinued. Subjects must not use any eye drops or ointment for treatment of eye symptoms, unless agreed to by a study doctor, at any time during the study and for  $\geq 1$  week after permanent discontinuation of study treatment.

### **Permitted Therapies/Products**

Subjects are permitted to receive prophylactic or supportive treatment as standard of care during the Treatment Period, per Investigator's discretion and institutional guidelines.

- Palliative radiation to known metastatic sites as long as the radiation field does not include a measurable lesion or interrupt treatment for more than 28 days from the planned date of administration (ie, 49 days from the last infusion date). Palliative radiotherapy to the thorax is permitted one week after infusion; however, the next infusion should start at least two weeks after the radiotherapy. Whenever possible, subjects should have a tumor assessment of the lesion(s) prior to receiving radiotherapy in order to rule out progression of disease. In cases of progression of disease, subjects should be discontinued from patritumab deruxtecan.
- Inhaled or topical steroids or intra-articular steroid injections
- Inactive/killed virus vaccinations
- Menstruating females may receive Depo-Provera or another suppressant of menses during the entire course of study treatment. In addition, after completion of study treatment, suppression of menses should be continued until the platelet count is  $\geq 50,000/\text{mm}^3$  without transfusion support
- Subjects taking warfarin should be monitored regularly for changes in PT or INR.

## 7. STUDY DRUG DISCONTINUATION AND DISCONTINUATION FROM THE STUDY

### 7.1. Discontinuation of Study Drug

The primary reason for the permanent discontinuation of patritumab deruxtecan treatment administration must be recorded. Reasons for treatment discontinuation include:

- Death
- Adverse Event
- Progressive Disease per RECIST v1.1
- Clinical Progression: provide date (ie, definitive clinical signs of disease progression, but a recent radiographic assessment did not meet the criteria for PD according to RECIST v1.1)
- Withdrawal by the subject (**to discontinue study drug**) NOTE: In this section this is only withdrawal for treatment with study drug and is NOT the same thing as a complete withdrawal from the study. Discuss with the subject that they will remain in the study (ie, continue with study visits and assessments, including survival follow-up).
- Physician Decision
- Lost to Follow-up (see Section 7.3 for details on when a subject is considered Lost to Follow-up)
- Pregnancy
- Protocol Deviation
- Study Termination by Sponsor
- Other

After study drug is permanently discontinued for any reason other than death or lost to follow-up, the subject will be treated as clinically indicated by the Investigator or referring physician.

The Investigator must discuss with the subject that their decision to permanently discontinue the study drug means the subject still agrees to continue into the Follow-up Period for onsite or modified follow-up visits. Subjects will be followed for disease progression, if applicable, and survival at regularly scheduled intervals (see Table 1.2).

#### Procedures for Discontinuation from Study Drug

The subject should be instructed to contact the Investigator or study site staff before or at the time study drug is discontinued.

If a subject is discontinued from the study drug:

- The reason(s) for discontinuation and the last dose date should be documented in the subject's medical record and eCRF;
- Due to an AE, the Investigator will follow the subject until the AE has resolved or stabilized;

- An EOT evaluation should be performed as described in the SoE (Table 1.2);
- A safety follow-up evaluation should be performed approximately 40 days (+7 days) after the last dose of study drug as described in the SoE (Table 1.2);
- If subject has discontinued study drug for any reason other than progressive disease or criteria specified below in Section 7.2, tumor assessments and survival follow-up should be continued as described in the SoE (Table 1.2);
- Long-term follow-up evaluations will be performed to assess survival as described in the SoE (Table 1.2).

The Investigator will complete and report the observations as thoroughly as possible up to the date of discontinuation, including the date of last dose. All procedures and tumor assessments specified for the EOT Visit will be conducted. See Table 1.2 for specific EOT procedures.

If a subject does not agree to continue to come to the study site, then a modified follow-up must be arranged to ensure the continued collection of endpoints and safety information. Options for modified follow-up are noted below.

### **Modified Follow-up Options**

The following modified follow-up options can be offered to the subject who does not agree to study visits at the study site. If a subject does not come back to the study site, every effort should be made to contact the subject to gain required information, such as the approaches listed below.

- Study personnel contacting the subject by telephone (may be quarterly, bi-annually, annually, or only at EOS)
- Study personnel contacting an alternative person (eg, family member, spouse, partner, legal representative, physician, or other healthcare provider)
- Study personnel accessing and reviewing the subject's medical information from alternative sources (eg, doctor's notes, hospital records)

Dates of the modified follow-up contact(s) should be recorded in the eCRF. See Section 7.2 for definition of withdrawal by the subject from the study (ie, withdrawal of consent).

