Subjects will continue to receive patritumab deruxtecan until documented disease progression per RECIST v1.1, clinical progression, unacceptable toxicity, withdrawal of consent by the subject, physician's decision, protocol deviation, pregnancy, lost to follow-up, study termination by the Sponsor, death, or other reasons. If progressive disease is suspected by Investigator tumor assessment, imaging must be submitted to BICR for expedited confirmation of disease progression. The decision to discontinue patritumab deruxtecan is according to Investigator judgement and should consider BICR assessment.

- The Follow-up Period will start upon permanent discontinuation of patritumab deruxtecan. After completion of the 40-day (+7 days) safety follow-up visit, subjects will be followed every 3 months for survival. Subjects who discontinue study treatment for any reason other than documented disease progression by BICR, death, lost to follow-up, or withdrawal of consent by the subject will continue to undergo tumor assessments at the same frequency of every 6 weeks ( $\pm 7$  days) from Cycle 1, Day 1 for the first 24 weeks then every 12 weeks ( $\pm 7$  days) during the Follow-up Period.

The primary analysis of ORR as assessed by BICR will be conducted after all enrolled subjects have either a minimum of 9 months of follow-up or have discontinued from the study earlier. The final analysis will occur after all subjects have discontinued from the study (see definition of overall End of Study [EOS] in Section 4.1.2).

The subject population is described in Section 5. A flow diagram of study activities is presented in Figure 1.1.

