#### 4.1.2. End of Study

The **primary completion date** is the date when all enrolled subjects have either a minimum of 9 months of follow up or have discontinued from the study earlier. This date will be used as the data cut-off (DCO) date for the primary analysis of the study. All subjects still on treatment and continuing to derive benefit from patritumab deruxtecan at the primary completion date will continue to follow the study SoE (Table 1.2) until the **overall End of Study (EOS)** is reached.

The subject's EOS is the date of their last study visit/contact.

Overall EOS will occur when:

- after the last subject last visit;
- all subjects have discontinued treatment and discontinued long-term survival follow-up or have died;
- an alternative study becomes available, for subjects continuing to derive benefit from treatment with patritumab deruxtecan, where the study drug is offered to these subjects;
- the study is discontinued by the Sponsor for other reasons (administrative, program-level or class-related). In the event the end of study is reached prior to last

subject last dose, the Sponsor will provide notification and rationale according to local regulatory requirements.

At the time of study closure, any subjects who are continuing treatment with patritumab deruxtecan and who are judged by the Investigator to have ongoing benefit may continue to receive treatment with patritumab deruxtecan through a rollover protocol or another mechanism consistent with local requirements.

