## **Survival Follow-up**

All subjects should be followed for survival at least every 3 months after discontinuing study drug (see [Table 1.2](#)). Survival monitoring will continue until the overall end of the study.

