#### **Time Period for Collecting Adverse Events, including AESIs and Serious Adverse Events**

All SAEs occurring after the subject signs the main ICF and up to 47 days after the last dose of study medication (ie, from the beginning of the Screening Period to the end of the Follow-up Period), whether observed by the Investigator or reported by the subject, will be recorded on the Adverse Event eCRF. Any serious, adverse event that may occur subsequent to the 40-day (+7 days) follow-up reporting period that the Investigator assesses as related to study drug should also be reported as an SAE. All SAEs will be followed until resolution, stabilization, the event is otherwise explained, or the subject is lost to follow-up.

When an AE of potential ILD (Section [8.4.1.2](#)) is observed after 47 days since the last dose of patritumab deruxtecan, the AE (serious or non-serious) should be reported and recorded in AE eCRF if it is considered related to patritumab deruxtecan.

All non-serious AEs occurring after the subject has taken the first dose of patritumab deruxtecan until 47 days after the last dose of study medication will be recorded on the Adverse Event eCRF.

Exacerbation of a pre-existing medical condition and symptom after the first dose of patritumab deruxtecan including increase in severity of the symptom will be recorded as an AE on the Adverse Event eCRF, unless it is a condition of NSCLC.

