#### 9.5.1.2. Secondary Efficacy Analyses

Secondary efficacy endpoints include ORR as assessed by Investigator per RECIST v1.1; best percentage change in the sum of diameters (SoD) of measurable tumors, disease control rate (DCR), DoR, TTR, and PFS as assessed by BICR and Investigator per RECIST v1.1, and OS.

A brief description of each endpoint is provided below:

- DoR is defined as the time from the date of the first documentation of response (confirmed CR or PR) to the date of the first documentation of PD or death due to any cause, whichever occurs first. Duration of response will be measured for responding subjects (subjects with confirmed CR or PR) only. Detailed censoring rules for DoR will be specified in the SAP.

- Best percentage change in the SoD of measurable tumors is defined as the percentage change in the smallest SoD from all post-baseline tumor assessments, taking as reference the baseline SoD.
- DCR is defined as the proportion of subjects who achieved a BOR of confirmed CR, confirmed PR, or SD.
- PFS is defined as the time from the start date of study treatment to the earlier of the dates of the first documentation of PD or death due to any cause. Detailed censoring rules for PFS will be specified in the SAP.
- TTR is defined as the time from the start date of study treatment to the date of the first documentation of response (confirmed CR or PR). The TTR will be measured for responding subjects (subjects with confirmed CR or PR) only.
- OS is defined as the time from the start date of study treatment to the date of death due to any cause. If there is no death reported for a subject before the DCO for the OS analysis, OS will be censored at the last contact date at which the subject is known to be alive.

Response endpoints (ORR and DCR) will be analyzed in the same manner as the primary efficacy endpoint. Distribution of time to event endpoints (DoR, PFS, and OS) will be estimated using the Kaplan-Meier method and results presented graphically. Median event time with a 2-sided 95% CI will be calculated using Brookmeyer and Crowley methods. In addition, the event-free probability at different time points (eg, 3, 6, 9 months, etc.) will be estimated with corresponding 2-sided 95% CIs using Greenwood's formula. TTR will be summarized using descriptive statistics.

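### Section 7.1 allows telephone contact yearly or only at End of Study, against the 3-monthly survival rule, so vital status may be out of date at the primary cut-off

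*Combined protocol and SAP*

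**What the plan says.** Section 8.3, Survival Follow-up, states: "All subjects should be followed for survival at least every 3 months after discontinuing study drug". Section 4.1.1 agrees: "After completion of the 40-day (+7 days) safety follow-up visit, subjects will be followed every 3 months for survival". Table 1.2 sets long-term follow-up at every 3 months with a window of ±14 days. The body of Section 7.1 refers to the same schedule, with follow-up for "survival at regularly scheduled intervals (see Table 1.2").

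For a subject who will not come to the site, Section 7.1 says that "a modified follow-up must be arranged to ensure the continued collection of endpoints and safety information". The list of options then opens with "Study personnel contacting the subject by telephone (may be quarterly, bi-annually, annually, or only at EOS"). Two further routes follow, an alternative person and the subject's medical information from other sources. Neither carries an interval.

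Section 9.5.1.2 gives the analysis rule for a subject with no reported death: "OS will be censored at the last contact date at which the subject is known to be alive". Under Section 4.1.2 the primary data cut-off comes when "all enrolled subjects have either a minimum of 9 months of follow up or have discontinued from the study earlier".

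**The concern.** Three of the four telephone intervals in Section 7.1 (reading bi-annually as twice a year) are longer than the interval required everywhere else. A site that agreed with a subject to telephone yearly, or only at End of Study, could claim to follow the protocol while breaking Section 8.3.

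No other clause clearly closes the gap. A subject who accepts rare calls has not withdrawn consent, because Section 7.2 requires refusal of every method. Nor is that subject lost to follow-up under Section 7.3, which requires two missed consecutive visits and failure of contact, so the public-record search there need not be triggered. No vital-status check before the primary cut-off appears in Sections 4.1.2, 8.3 or 9.1 or in Table 10.6.

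At stake is the completeness of OS at the primary analysis, including the Kaplan-Meier median and the event-free probabilities of Section 9.5.1.2. How up to date those data are would depend on what each site arranged.

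**Working it through.** **The plan's own figures.** The documents give no OS planning value, event count or expected share of subjects on modified follow-up. The only power figure is for ORR: 210 per arm, 26.4% against 37%, two-sided 5%, about 91%. The exact binomial calculation, rejecting at 69 or more responders, gives 90.7%. ORR does not depend on survival contact.

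**Timing.** Inputs: 12 months of enrolment (Section 4.1.4), cut-off 9 months after the last enrolment (Section 4.1.2), and median time on treatment of 4.5 months in the Phase 1 study (Section 2.2), used only as illustration. Enrolment is assumed uniform and calls are counted from drug stop.
- Cut-off falls between 9 months (last enrolled) and 9 + 12 = 21 months (first enrolled) after a subject's start.
- Annual call: 4.5 + 12 = 16.5 months. This is after cut-off for subjects enrolled in the last 16.5 − 9 = 7.5 of the 12 months.
- Twice-yearly call: 4.5 + 6 = 10.5 months. This is after cut-off for those enrolled in the last 1.5 months.
- EOS-only call: the planned total is 26 months against a cut-off near month 21, so the call would come about 5 months late.

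**Effect on median OS, first model.** One million simulated subjects, with accrual and cut-off as above and exponential time on drug with median 4.5 months. A share f of subjects who stop drug alive go to modified follow-up. Those with unknown status are censored at a last contact soon after stopping. Assumptions not in the documents: f; hazards of 0.02 per month on drug and 0.11 off drug; decliner hazard ratios of 0.5, 1 and 2. The constant-hazard case borrows the median of about 10 months that Section 2.3 gives for standard therapy. Entries are median OS in months with full information → as analysed.

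| Scenario | f = 5% | f = 10% | f = 20% |
|---|---|---|---|
| No contact, no deaths found: constant hazard | 10.02 → 10.02 | 10.04 → 10.04 | 10.03 → 10.03 |
| Same, hazard rises off drug | 11.25 → 11.34 | 11.22 → 11.40 | 11.25 → 11.64 |
| Same, decliners at twice the hazard | 11.05 → 11.26 | 10.85 → 11.26 | 10.49 → 11.29 |
| Same, decliners at half the hazard | 11.43 → 11.37 | 11.62 → 11.51 | 12.03 → 11.83 |
| Deaths found, living not updated: constant hazard | 10.02 → 9.91 | 10.04 → 9.82 | 10.03 → 9.60 |
| Same, hazard rises off drug | 11.25 → 11.17 | 11.22 → 11.05 | 11.25 → 10.93 |
| Same, decliners at half the hazard | 11.43 → 11.27 | 11.62 → 11.30 | 12.03 → 11.35 |

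At f = 10% with no deaths found, between 4.3% and 7.0% of deaths before cut-off go unrecorded. Annual calls roughly halve the shift when hazard rises off drug (11.25 → 11.47 at f = 20%). Three-monthly contact for everyone leaves at most 0.03 months in every scenario.

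**Second model, as a check.** OS is time on drug (median 4.5 months) plus post-treatment survival (median 6 months), with decliners censored 40 days after stopping and no deaths found.
- f = 5%, decliners at a 3-month post-treatment median: 12.4 → 12.7, about 5 deaths per 210 unrecorded.
- f = 10%, equal survival: 12.7 → 13.0, about 10 of 121 deaths unrecorded.
- f = 10%, decliners at 3 months: 12.2 → 12.8, about 11 of 125.
- f = 15%, decliners at 3 months: 12.0 → 12.8, about 16 of 126.
- f = 10%, decliners at 12 months: 13.1 → 13.0.
- f = 10%, equal survival, half the deaths found by other routes: 12.65 → 12.69.

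**The case against.** A reader might infer that deaths in this group will be missing at the cut-off and that OS will therefore be overstated. The documents do not support either as a consequence. The long intervals attach only to telephoning the subject. The other two routes have no such limit, Section 7.1 asks for every effort to obtain the required information, and modified follow-up must secure endpoint data. Censoring at the last date known alive removes living and dead subjects together, so overstatement needs a higher hazard after drug stop or sicker decliners, and deaths that no other route finds. If deaths are found while living subjects are not updated, OS is understated.

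A reader might also infer a gap in safety collection, because a quarterly call comes after the period in which non-serious events "until 47 days after the last dose of study medication will be recorded on the Adverse Event eCRF". That does not stand. Section 7.1 separately calls for a safety evaluation about 40 days (+7) after the last dose, and nothing says the telephone schedule replaces it. Nor can the 9-month follow-up statement be called untrue, since the plan does not define follow-up by contact.

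The consequences are limited as well. OS is descriptive, with no test and no comparison of arms, and a later final analysis can take in deaths learned at End of Study. In the second model the sampling range of the median with 210 subjects is about 11.0 to 14.5 months, wider than any shift shown.

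All of this stands and limits the claim. It does not remove the conflict: the alternative routes are options with no interval, and none is tied to the cut-off.

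**Conclusion.** The conflict between the Section 7.1 telephone intervals and the 3-monthly rule is plain on the text. Combined with a cut-off that can fall 9 months after enrolment and the absence of a vital-status check, it means some subjects who decline site visits may have out-of-date vital status at the primary analysis.

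OS may then be biased, plausibly upward, but the direction is not fixed by the documents. For f of 5% to 15%, an assumed range, the shifts in median OS are mostly a few tenths of a month. The largest upward shift is about 0.8 months, at f = 15% with markedly sicker decliners and no deaths found. Across all scenarios up to f = 20%, the first model runs from about 0.7 months down to 0.8 months up. If few subjects take this option, the effect is negligible. ORR and its test are untouched. This is a modest, cheaply removed weakness in a descriptive secondary endpoint.

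**What to change.** In Section 7.1, replace the bracketed telephone intervals with the Table 1.2 interval, every 3 months ±14 days. State that it may be met by telephone or, where the subject accepts less personal contact, through the alternative person or medical records already listed.

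In Section 8.3, add a vital-status check around the primary data cut-off, by the same routes, for every subject not known to have died. It must update living subjects as well as find deaths, since finding deaths alone biases OS downward. Report completeness of OS follow-up with the primary analysis.

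The cost is a sentence in each section and a few extra calls or record checks per affected subject. No visits or procedures are added, and a subject who prefers little personal contact need not be called more often.

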## **7.2. Subject Withdrawal/Discontinuation from the Study**

Subjects may discontinue from the study for any of the following reasons:

- Death
- Withdrawal by the subject (**from the study**) NOTE: This indicates that the subject withdraws consent and refuses to undergo any further study procedures or be followed for long-term survival.
- Lost to Follow-up (see Section 7.3 for details on when a subject is considered lost to follow-up)
- Study Termination by Sponsor
- Other

If the reason for study discontinuation is the death of the subject, the options for categorizing the primary cause of death are progressive disease or adverse event. If reason of death is unknown every effort should be made to obtain the primary cause of death. Only one AE will be recognized as the primary cause of death.

Only subjects who refuse all of the following methods of follow-up will be considered to have withdrawn consent from study participation (ie, from the interventional portion and follow-up):

- Attendance at study visits per protocol
- Study personnel contacting the subject by telephone
- Study personnel contacting an alternative person
- Study personnel accessing and reviewing the subject's medical information from alternative sources

If the subject refuses all of the above methods of follow-up, the Investigator should personally speak to the subject to ensure the subject understands all of the potential methods of follow-up. If the subject continues to refuse all potential methods of follow up, the Investigator will document this as a withdrawal of consent (from the interventional portion and follow-up).

